10.1 Investigator's Global Assessment (IGA)

At every study visit, overall severity of acne using a five-point scale from 0 = clear to 4 = severe will be conducted at each visit. This is a static morphological scale that refers to a point in time and not a comparison to Baseline. Subjects must have an IGA score of 3 (moderate) or 4 (severe) at Baseline.

0	Clear	Absence of active disease with no inflammatory or non-inflammatory lesions.
1	Almost Clear	Rare non-inflammatory lesions with no more than one small inflammatory lesions.
2	Mild	Some non-inflammatory lesions with no more than a few inflammatory lesions (papules/pustules only; no nodular/cystic lesions).
3	Moderate	Up to many non-inflammatory lesions and may have some inflammatory lesions but no more than one nodular/cystic lesion.
4	Severe	Up to many non-inflammatory lesions and inflammatory lesions but no more than a few nodular/cystic lesions.

10.2 Acne Lesion Counting

The number of inflammatory lesions (papules, pustules, and nodules) and non-inflammatory lesions (open and closed comedones) on the face vertically from the hairline to mandible rim and horizontally from ear to ear, including those on the nose will be counted to determine subject eligibility at Visit 1. Subjects must have at least 30 to a maximum of 75 inflammatory lesions and 30 to a maximum of 100 non-inflammatory lesions on the face (which can include the nose) at Baseline.

Lesions are defined as follows:

- Comedones- open (blackheads) and closed (whiteheads).
- Papules- raised inflammatory lesions with no visible purulent material.
- Pustules- raised inflammatory lesions with visible purulent material.
- Nodules- Any circumscribed, inflammatory masses greater or equal to 5 mm in diameter with or without cystic changes.

10.3 Fitzpatrick Skin Type Assessment

At Visit 1, the investigator or designee will document the subject's skin phototype (I-VI) using the Fitzpatrick Skin Type Assessment as described below:

FITZPATRICK SKIN TYPE		
Skin Phototype	Typical Features	Tanning ability
I	Pale white skin, blue/hazel eyes, blond/red hair	Always burns, does not tan
II	Fair skin, blue eyes	Burns easily, tans poorly
III	Darker white skin	Tans after initial burn
IV	Light brown skin	Burns minimally, tans easily
V	Brown skin	Rarely burns, tans darkly easily
VI	Dark brown or black skin	Never burns, always tans darkly

10.4 Local Skin Reactions (LSRs)

At every study visit, the investigator or designee will document the severity of the following LSRs known to be associated with application of topical steroids:

- Telangiectasia
- Skin atrophy
- Striae rubrae

A five-point ordinal scale will be used to assess the severity of these reactions (0 = none, 1 = trace, 2 = mild, 3 = moderate, and 4 = severe).

In addition, the investigator or designee will evaluate the severity of the following LSRs known to be associated with acne vulgaris, using the five-point ordinal scales described below:

- Erythema
- Edema
- Scaling/dryness

Erythema:

0	None
1	Minimal – barely perceptible erythema
2	Mild – predominantly minimal erythema (pink) in the treated area with or without a few isolated areas of more intense erythema
3	Moderate – predominantly moderate erythema (red) in the treated area with or without a few isolated areas of intense erythema (bright red)
4	Severe – predominantly intense erythema (bright red) in the treated area with or without a few isolated areas of very intense (fiery red) erythema

Edema:

0	None
1	Minimal – scant, rare edema
2	Mild – easily seen edema, minimally palpable, involving up to 1/3 of the Treatment Area
3	Moderate – easily seen edema and typically palpable, involving between 1/3 to 2/3 of the Treatment Area
4	Severe – easily seen edema, indurated in some areas, involving over 2/3 of the Treatment Area

Scaling/dryness:

0	None
1	Minimal – barely perceptible desquamation
2	Mild - limited areas of fine desquamation in up to 1/3 of the treatment area
3	Moderate – fine desquamation involving 1/3 to 2/3 of the treatment area or limited areas of coarser scaling
4	Severe – coarser scaling involving more than 2/3 of the treatment area or limited areas of very coarse scaling

In addition, subjects will be asked to rate the severity of the following LSRS that occurred in the treatment area since the last visit, using the four-point ordinal scales described below:

- Stinging/burning
- Pruritus

Stinging/burning:

0	None
1	Minimal, barely perceptible – tolerable and little discomfort
2	Moderate – tolerable, but causes some discomfort
3	Severe – very uncomfortable or intolerable

Pruritus (itching):

0	None - no evidence of itching
1	Mild - only aware of itching at times, only present when relaxing, not present when focused on other activities
2	Moderate - often aware of itching, annoying, sometimes disturbs sleep and daytime activities
3	Severe -constant itching, distressing; frequent sleep disturbance, interferes with activities

These LSRs will be collected independently of AEs. Only LSRs that require medical intervention (e.g., prescription medication) or require withholding the application of the test articles will be documented as AEs. Any LSRs that are not listed above will be recorded as AEs.

11. PHOTOGRAPHY

Photography documentation is required in this study. Photographs taken as part of this study will be used to document the effects of treatment, AEs, or other findings during the trial. Color photographs (both sides of the face and the front of the face) of the areas with acne lesions of all enrolled subjects will be performed at the Baseline Visit prior to application of the test articles and at Visits 2, 3, and 4. The study sites will be provided with suggested guidelines to assist them in taking standardized photographs. In addition, investigators at all study sites may take photos as they deem appropriate to document the clinical status of the subject (e.g., an AE, etc.). Photographs taken for this study are for informational purposes only and are not to assist in grading or for any other assessment.

Note: Subjects may decline to have photographs taken during the conduct of the study. If a subject initially consents to photographs, then declines further photography, the Sponsor may use the photographs taken under consent for the purposes noted above.

12. LABORATORY TESTS

12.1 Urine Pregnancy Tests (UPTs)

The UPT will be performed at the study site if the site is registered and conforms to Clinical Laboratory Improvement Amendments (CLIA) regulations for such testing (site possesses at a minimum a current valid CLIA Certificate of Waiver) or at an appropriately registered reference laboratory. A UPT will be performed at every visit on all WOCBP (see Section 5.1.1 for definition). The investigator will report the UPT results on the CRFs, in the subject's medical records and, if applicable, in independent records maintained at the study site. The UPT used must have a minimum sensitivity of 25 mIU of β -HCG/mL of urine.

13. END OF STUDY CRITERIA

At the end of each subject's participation in the study, the investigator will complete an End of Study form for all completed and discontinued subjects.

13.1 Completion of the Study

Each subject who completes the 12-week course of treatment as specified in this protocol will have completed the study.

13.2 Subject Discontinuation

A subject may be withdrawn from the study prior to completion for any of the following reasons:

- Whenever the subject or the subject's parent/guardian decides it is in the subject's best interest to be withdrawn, Note: if the subject or parent/guardian decides to withdraw from the study due to an AE then it should be classified as withdrawal due to an AE.
- Whenever the investigator decides it is in the subject's best interest to be withdrawn
- AEs
- Worsening of condition or treatment failure (in the opinion of the investigator)
- Noncompliance
- Pregnancy
- Lost to follow-up
- Sponsor administrative reasons

If a subject withdraws prematurely during the 12-week treatment period for any reason, the Visit 4 procedures should be completed at that time. Subjects who withdraw prematurely will not be replaced. When a subject is withdrawn from the study for a treatment-related AE (i.e., possibly, probably or definitely related as defined in Section

14), when possible, the subject should be followed until resolution or stabilization of the AE.

13.3 Study Termination

The study may be terminated by the investigator or the Sponsor. If, in the opinion of the investigator, clinical observations made during the study suggest that it may be unwise to continue, he or she may stop the study. A study termination by the investigator will be reported to the Sponsor.

In addition, a written statement fully documenting the reasons for this action will be submitted to the Sponsor by the investigator within five (5) working days.

In the event that the Sponsor chooses to discontinue or terminate the study, appropriate notification will be given to the investigator.

14. ADVERSE EVENT REPORTING

An **adverse event** (AE) is any untoward medical occurrence associated with the use of a drug in humans, whether or not considered drug related.

An AE (also referred to as an adverse experience) can be any unfavorable and unintended sign (e.g., an abnormal laboratory finding), symptom, or disease temporally associated with the use of a drug, without any judgment about causality. An AE can arise from any use of the drug (e.g., off-label use, use in combination with any drug) and from any route of administration, formulation, or dose, including an overdose.

Information on the medical condition of subjects should begin following the subject's written consent/assent to participate in the study and a medical history should be taken at screening. During any wash out and baseline periods, any changes in the health of subjects should be recorded as changes in medical history unless the event occurred as a result of a study-related procedure and is unanticipated, in such cases, the event should be recorded as an AE and reported to the Institutional Review Board (IRB) as an "unanticipated problem" in accordance with local procedures. Other changes in subject health information becomes AE data when the subject begins dosing with the test article and therefore AE data should be collected from the date of the first dose of test article. These data are considered treatment-emergent AEs.

Timely and complete reporting of all AEs assists CRO in identifying any untoward medical occurrence, thereby allowing:

- 1) protection of the safety of study subjects;
- 2) a greater understanding of the overall safety profile of the test article;
- 3) recognition of dose-related test article toxicity;
- 4) appropriate modification of study protocols;
- 5) improvements in study design or procedures; and

6) adherence to worldwide regulatory requirements.

Test article is defined as a pharmaceutical form of an active ingredient or vehicle/placebo being tested or used as a reference in the study, whether blinded or unblinded. AEs may be either spontaneously reported or elicited during questioning and examination of a subject. All AEs must be completely recorded on the AE CRF. If known, the investigator should report the diagnosis of the underlying illness or disorder, rather than its individual symptoms. Subjects experiencing AEs that cause interruption or discontinuation of test article, or those experiencing AEs that are present at the end of their participation in the study should receive follow-up as appropriate. If possible, report the outcome of any AE that caused permanent discontinuation or that was present at the end of the study particularly if the AE is considered by the investigator to be treatment-related (i.e., definitely, probably, or possibly related to test article).

14.1 Adverse Event (AE)

All AEs must be recorded on the AE CRF. AEs should be followed to resolution or stabilization (if possible), and reported as serious adverse events (SAEs) if they become serious.

LSRs that have been reported in subjects treated with CB-03-01 creams (0.1%-1% concentration) include (with decreasing frequency) erythema, pruritus, scaling/dryness, skin atrophy, striae rubrae, stinging/burning, edema, and telangiectasia; however most LSRs were typically of minimal to mild severity. No subjects discontinued treatment due to these LSRs.

AEs that have been reported in subjects treated with CB-03-01 creams (0.1-1% concentration) were minimal, typically mild in severity, and most were recovered/resolved without sequelae at the end of the study. Only two AEs in one (1) subject were judged as probably or possibly related to treatment; both of these treatment-related AEs (burning and cold at application site) were mild in severity. Two SAEs have been reported to date; both were not related to treatment and were resolved at the end of the study. In addition, one subject discontinued early from the study due to an AE (urinary tract infection), which was not related to treatment.

The investigator will instruct the subject to report any AEs that may occur during the study. At each visit, the investigator should ask the subject, in non-directive fashion, about any change in the subject's overall condition since the previous visit.

The severity of each AE, as judged by the investigator, will be recorded on the appropriate AE CRF and will be graded according to the following scale:

Mild - The AE is transient and easily tolerated by the subject.

Moderate - The AE causes the subject discomfort and interrupts the subject's usual activities.

Severe - The AE causes considerable interference with the subject's usual activities, and may be incapacitating or life-threatening.

The investigator must determine the relationship of the AE to the test article according to the following categories:

Definite - An event that follows a reasonable temporal sequence from administration of the test article; that follows a known or expected response pattern to the test article; and that is confirmed by improvement on stopping or reducing the dosage, and reappearance of the event on repeated exposure (re-challenge).

Probable - An event that follows a reasonable temporal sequence from administration of the test article; that follows a known or expected response pattern to the test article; and that is confirmed by improvement on stopping or reducing the dosage of the test article; and that is unlikely to have been caused by concurrent/underlying illness or other drugs, procedures, or other causes.

Possible - An event that follows a reasonable temporal sequence from administration of the test article; that follows a known or expected response pattern to the test article; but may have been caused by concurrent/underlying illness, other drug, procedure, or other causes.

Unlikely - An event that does not follow a reasonable temporal sequence from administration of the test article; that does not follow a known or expected response pattern to the test article, or most likely was caused by concurrent/underlying illness, other drug, procedure, or other causes, because of their known effects.

Not Related - An event almost certainly caused by concurrent/underlying illness, other drug, procedure, or other causes.

The investigator should categorize the outcome of the AE according to the following categories:

Fatal - Termination of life as a result of an AE.

Not Recovered/Not Resolved - AE has not improved or the subject has not recuperated.

Recovered/Resolved - AE has improved or the subject has recuperated.

Recovered/Resolved with Sequelae - subject recuperated but retained the pathological conditions resulting from the prior disease or injury.

Recovering/Resolving - AE is improving or the subject is recuperating.

Unknown - Not known, not observed, not recorded or subject refused.

The investigator should report the action taken with the test article due to the AE according to the following categories:

Dose Not Changed - An indication that a medication schedule was maintained.

Dose Increased - An indication that a medication schedule was modified by addition; either by changing the frequency, strength or amount.

Dose Reduced - An indication that a medication schedule was modified by subtraction, either by changing the frequency, strength or amount.

Drug Interrupted - An indication that a medication schedule was modified by temporarily terminating a prescribed regimen of medication.

Drug Withdrawn - An indication that a medication schedule was modified through termination of a prescribed regimen of medication.

Not Applicable - Determination of a value is not relevant in the current context.

Unknown - Not known, not observed, not recorded, or refused.

The investigator should report any other action taken due to the AE.

An **adverse reaction** is any AE caused by a drug. Adverse reactions are a subset of all suspected adverse reactions for which there is reason to conclude that the drug caused the event. For the purposes of prescription drug labeling, the term adverse reaction means an undesirable effect, reasonably associated with the use of a drug that may occur as part of its pharmacological action or may be unpredictable in its occurrence.

A **suspected adverse reaction** is any AE for which there is a reasonable possibility that the drug caused the event.

For the purposes of IND safety reporting, "reasonable possibility" means there is evidence to suggest a causal relationship between the drug and the AE. A suspected adverse reaction implies a lesser degree of certainty about causality than adverse reaction, which means any AE caused by a drug.

An AE or suspected adverse reaction is considered “unexpected” if it is not listed in the investigator brochure or is not listed at the specificity or severity that has been observed; or, if an investigator brochure is not required or available, is not consistent with the risk information described in the general investigational plan or elsewhere in the current application. For example, under this definition, hepatic necrosis would be unexpected (by virtue of greater severity) if the investigator brochure referred only to elevated hepatic enzymes or hepatitis. Similarly, cerebral thromboembolism and cerebral vasculitis would be unexpected (by virtue of greater specificity) if the investigator brochure listed only cerebral vascular accidents. "Unexpected," as used in this definition, also refers to AEs or suspected adverse reactions that are mentioned in the investigator brochure as occurring with a class of drugs or as anticipated from the pharmacological properties of the drug, but are not specifically mentioned as occurring with the particular drug under investigation.

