Study endpoints that are SAEs (e.g., all-cause mortality) must be reported in accordance with the protocol unless there is evidence suggesting a causal relationship between the drug and the event (e.g., death from anaphylaxis). In this case, the investigator must immediately report the event to the Sponsor. In addition, such information should also be provided to the site’s respective IRB per their governing guidelines for SAE reporting.

If only limited information is initially available, follow-up reports are required. Should the investigator become aware of an SAE (regardless of its relationship to test article) that occurs within 30 days after stopping the test article, the SAE must be reported in accordance with procedures specified in this protocol. In the event of death, if an autopsy is performed, a copy of the report should be sent to Sponsor, if available.

As required, CRO will notify participating investigators of all suspected adverse reactions that are serious and unexpected. This notification will be in the form of an IND safety report of potential serious risks as soon as possible but no later than 15 calendar days after the Sponsor determines that the information is “reportable” according to the criteria listed in 21 CFR Section 312.32. These are:

- i) Serious and unexpected suspected adverse reactions,
- ii) Findings from other studies including epidemiological studies, pooled analyses, or other clinical studies that suggest a significant risk in humans exposed to the test articles,
- iii) Findings from animal or in vitro tests that suggest a significant risk to humans exposed to the test articles or reports of significant organ toxicity at or near the expected human exposure, and
- iv) Clinically important increases in the rate of occurrence of serious suspected adverse reactions.

Upon receiving such notices, the investigator must review and retain the notice with the Investigator Brochure and immediately submit a copy of this information to the responsible IRB according to local regulations. The investigator and IRB will determine if the informed consent/assent requires revision. The investigator should also comply with the IRB procedures for reporting any other safety information. Where required, submission of safety updates by the investigator to Health Authorities should be handled according to local regulations.

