### 6.10.2 Adverse events

All AEs will be coded using the Medical Dictionary for Regulatory Activities (MedDRA) and listed. The version of the dictionary used for coding will be reported in the clinical study report.

AEs will be classified as Pre-Treatment AEs (PTAEs) and Treatment Emergent AEs (TEAEs), according to the period of occurrence, as follows:

- PTAEs: all AEs occurring before the first dose of the test article and not worsening after the first dose of the test article;
- TEAEs: all AEs occurring or worsening after the first dose of the test article.

Individual TEAEs and PTAEs will be listed by treatment group ([Listing 16.2.7.1](#), [Listing 16.2.7.2](#)).

No summary table will be provided for PTAEs.

TEAEs will be summarised by treatment group and overall.

- The number and percentage of subjects with any TEAE and the number of TEAEs will be presented overall ([Table 14.3.1.1](#)) and by SOC and PT ([Table 14.3.1.2](#));
- The number and percentage of subjects with any TEAE by relationship and the number of TEAEs by relationship will be presented ([Table 14.3.1.1](#));
- The number and percentage of subjects with any TEAE related to the IMP and the number of TEAEs related to the IMP will be presented by SOC and PT ([Table 14.3.1.3](#));
- The number and percentage of subjects with any TEAE by severity and the number of TEAEs by severity will be presented overall ([Table 14.3.1.1](#)) and by SOC and PT ([Table 14.3.1.4](#));
- The number and percentage of subjects with any TEAE leading to discontinuation and the number of TEAEs leading to discontinuation will be presented ([Table 14.3.1.1](#)).

Serious TEAEs will be summarised by treatment group and overall.

- The number and percentage of subjects with any Serious TEAE and the number of Serious TEAEs will be presented overall ([Table 14.3.1.1](#)) and by SOC and PT ([Table 14.3.1.5](#));

- The number and percentage of subjects with any Serious TEAE by relationship and the number of Serious TEAEs by relationship will be presented (Table 14.3.1.1);
- The number and percentage of subjects with any Serious TEAE related to the IMP and the number of Serious TEAEs related to the IMP will be presented by SOC and PT (Table 14.3.1.6);
- The number and percentage of subjects with any Serious TEAE leading to discontinuation and the number of Serious TEAEs leading to discontinuation will be presented (Table 14.3.1.1).

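### Every related grade on the causality scale requires a known or expected reaction pattern, so an AE that is neither is left out of the related-TEAE tables

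*Protocol*

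**What the plan says.** Use of the scale in Protocol 14.1 is mandatory for every AE. All three upper grades ask for reasonable timing and for a recognised pattern.

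- Definite: the event must follow "a known or expected response pattern to the test article; and that is confirmed by improvement on stopping or reducing the dosage, and reappearance" on re-challenge.
- Probable: the definition asks for "a known or expected response pattern to the test article; and that is confirmed by improvement on stopping or reducing the dosage of" (the cream), and other causes must be unlikely.
- Possible: an event "that follows a known or expected response pattern to the test article; but may have been caused by concurrent/underlying illness" or another cause.
- Unlikely: its listed features include an event "that does not follow a known or expected response pattern to the test article, or most likely was caused by concurrent/underlying illness" or another cause.
- Not Related: another cause is almost certain.

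Later in the same section, a suspected adverse reaction "is any AE for which there is a reasonable possibility that the drug caused the event". Whether an event is unexpected is defined on its own, by reference to the investigator brochure.

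Protocol 13.2 gives the meaning of treatment-related: "treatment-related AE (i.e., possibly, probably or definitely related as defined in Section" 14. The opening part of Section 14 uses the same three grades. SAP 6.10.2 plans a table by SOC and PT of "The number and percentage of subjects with any TEAE related to the IMP" (Table 14.3.1.3), with a counterpart for serious TEAEs (Table 14.3.1.6). It does not say which grades count as related.

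**The concern.** The scale mixes two questions: whether the cream caused the event, and whether the event was already recognised or anticipated. The second should not decide the first. A reaction that starts soon after dosing, resolves on stopping and has no other explanation is good evidence of causation even if nobody has seen it before.

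Safety is part of the primary objective (Protocol 3). Recorded related experience before this trial is thin: Protocol 14.1 reports two mild application-site AEs in one subject, besides the listed local skin reactions. Protocol 10.4 sends any unlisted local reaction to the AE form, so it is graded on this scale too. What is at stake is whether the related-TEAE summaries can show a reaction that is new to the product.

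**Working it through.** No figure in the plan needs reproducing. The check treats the grade definitions as rules and follows the result into the tables.

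**Step 1. Conditions for each related grade (Protocol 14.1).**

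| Grade | Reasonable timing | Known or expected pattern | Improves on stopping or reducing | Recurs on re-challenge | Other cause |
|---|---|---|---|---|---|
| Definite | required | required | required | required | not mentioned |
| Probable | required | required | required | not mentioned | must be unlikely |
| Possible | required | required | not mentioned | not mentioned | may be the cause |

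**Step 2. Test case.** Take an event with reasonable timing and no known or expected pattern. Let the other three criteria vary, each yes or no: 2 × 2 × 2 = 8 combinations. The pattern column is required in all three rows, so 0 of 8 reach a related grade. That includes the combination with improvement on stopping, recurrence on re-challenge and no other cause.

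A paired case shows that the pattern clause alone does this. With good timing, improvement on stopping, other causes unlikely and a recognised pattern, the event is Probable. Without the recognised pattern, and with nothing else changed, it has no related grade.

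**Step 3. Where the event goes.** The clauses under Unlikely are joined ambiguously.

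- Read as alternatives, lack of a pattern is enough and the event is Unlikely.
- With the timing and pattern clauses read together, an event with good timing and no likely other cause is not Unlikely. It is not Not Related either, since that needs an almost certain other cause. It fits no grade.

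Both readings place it outside Definite, Probable and Possible.

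**Step 4. Compare with the rest of 14.1.** The definition of a suspected adverse reaction asks only for a reasonable possibility of causation. The definition of an adverse reaction allows for unpredictable ones. Neither has a pattern condition. The Step 2 event can be a suspected adverse reaction by definition and still be ungradable as related.

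**Step 5. Effect on the tables.** SAP 1.1 reports no change from the protocol, so the protocol's meaning of treatment-related (13.2 and Section 14) is the natural one for SAP 6.10.2. On that meaning the event is absent from Table 14.3.1.3 and, if serious, from Table 14.3.1.6. It remains in the all-TEAE table by SOC and PT (14.3.1.2), the severity table (14.3.1.4), the counts by relationship (14.3.1.1) and the listings. Those counts by relationship are not broken down by PT, so no planned summary shows which PTs were graded Unlikely.

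**Step 6. Illustration on assumed rates.** Take about 732 / 2 = 366 subjects on active (SAP 2.4, 1:1) and a drug-caused, neither known nor expected reaction with true incidence p. Expected cases are 366p; the chance of at least one is 1 − (1 − p)^366.

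| Assumed p | Expected cases | Chance of at least one |
|---|---|---|
| 0.5% | 1.83 | 0.840 |
| 1% | 3.66 | 0.975 |
| 2% | 7.32 | 0.999 |

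This shows only that such an event could plausibly arise in a trial of this size. It says nothing about how sites actually graded, and Steps 1 to 5 do not rest on it.

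**The case against.** The best reply is that little depends on this grade. The trial is randomized and vehicle-controlled, so a new reaction would show as a difference between arms in the all-TEAE tables, with no need for investigator attribution. That stands, and it confines the defect to the related subset tables.

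The condition is also known or expected, not known alone. A reaction not yet seen but predictable from antiandrogen or weak glucocorticoid pharmacology (Protocol 1), or from topical steroid use (Protocol 10.4), may qualify. That stands too: the point covers only events that are neither. Investigators may use judgement beyond the text, but no section provides for it.

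Four stronger inferences are tempting, and the documents do not support them.

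- *The scale cannot yield an event that is both suspected and unexpected, so the notice in Protocol 14.2 ("CRO will notify participating investigators of all suspected adverse reactions that are serious and unexpected") would never be triggered.* Protocol 14.1 also calls an event unexpected when it is anticipated from the pharmacology but not listed for this drug, or is more severe or specific than listed. Such an event can be Possible or Probable and still be unexpected.
- *The scale feeds expedited reporting.* Protocol 14.2 requires immediate reporting of all SAEs whatever the relationship, with a separate assessment of reasonable possibility. The reporting clock runs from the sponsor's determination.
- *The grade decides who is followed up.* Protocol 14.1 asks that AEs be followed to resolution or stabilization if possible, without regard to relatedness. Section 14 also covers any AE that interrupts or stops treatment or is present at the end. The sentence in 13.2 adds emphasis and is not the gate.
- *Every new reaction is capped at Unlikely.* That is one of the two readings in Step 3.

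**Conclusion.** The point holds in a limited form. As written, the scale denies a related grade to any AE that is neither known nor expected, however strong the other evidence, and this departs from the reasonable-possibility definition in the same section. The consequence is incomplete related-TEAE tables, mainly for non-serious reactions. Detection of a difference between arms, SAE reporting and AE follow-up are not shown to be impaired.

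The conclusion rests on two assumptions: that investigators apply the text literally, and that the SAP means by related what the protocol means by treatment-related. The number of events affected cannot be derived from the documents.

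**What to change.** In Protocol 14.1, remove the pattern condition from Possible and Probable and delete the matching clause from Unlikely. Relatedness then follows reasonable possibility, and expectedness is left to its own definition. A recognised pattern can still support a grade without being required for it. The unpatterned event in the paired case of Step 2 would become Probable.

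SAP 2.4 already reports 732 subjects enrolled, so new wording cannot change grades already given. The usable remedy for this trial lies in the SAP, which is to be finalized before database lock:

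- state in 6.10.2 which grades count as related to the IMP;
- add one supportive table by SOC, PT and arm of TEAEs graded anything other than Not Related.

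The cost is a few words in 14.1, one definition and one more table. Where the new wording is used, the reported related-TEAE rate may rise slightly in both arms.
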